## 8) Potential benefits to subjects\*

### a) Relaxation

- i) *Passiflora incarnata* has been found to have anxiolytic properties and might reduce sympathetic tone. The participants may note a sense of well-being and relaxation after participating in the research
- ii) Meditation has been found to improve well-being in medical students. The participants may note an improved sense of well-being and sense of relaxation after participating in the research
- iii) These relaxation effects are likely and should last for the rest of the research day

## 9) Provisions to protect the privacy interests of subjects

- a) Initial data to be gathered only by [name] or [name] include information regarding age, sex, past medical history (i.e. previous medical diagnoses), and medication usage (*See Attachment D*). This information will be linked to the

UB HRP-503 TEMPLATE: Protocol

PROTOCOL TITLE: Investigating the short-term effects of *Passiflora incarnata* and mobile audio-guided meditation on blood pressure and heart rate in naturopathic medical students

PROTOCOL DATE: 3/28/19

Template Revised: June 14, 2010

- participants' de-identified code. The code will only be linked back to the patient's name on a password-protected Excel sheet on the password-protected University computer belonging to the investigators.
- b) Blood pressure and heart rate readings will be linked to the participants' de-identified code. The code will only be linked back to the patient's name on a password-protected Excel sheet on the password-protected University computer belonging to the investigators.
  - c) The adverse event survey (*see Attachment C*) will be linked to the participants' de-identified code. The code will only be linked back to the patient's name on a password-protected Excel sheet on the password-protected University computer belonging to the investigators.
  - d) Only [name] and [name] will have access to the participants' data. The student RAs will not have access to the subject's data with the exception of their blood pressure and heart rate readings, as the student RAs will be collecting these measurements.
  - e) Being that the participants are students, they will be assured that their data will be kept completely confidential and stored only on password-protected excel sheets and password-protected computers. They will be assured that their questionnaire answers will not be used for any other academic means other than the intended research. They will be assured that the inclusion/exclusion criteria checklist, initial data questionnaire, and adverse events questionnaire will not be accessible by the student RAs. They will be assured that their willingness to participate in the research will in no way affect the way that they are treated in the classroom by their professors. They will be assured that choosing to participate or not to participate in the research will not affect their grade in their naturopathic classes. There will be no extra credit given for participating in the research.
  - f) Since naturopathic medical students will be studied in groups in one large room, the subjects will be informed that his/her classmates in the same room will know that he/she is participating in the study. To minimize any privacy risks, all medical information will be collected in private before the day of the study. On the day of the study, we will not read the participants' blood pressure and heart rate readings out loud. We also will ask the participant to write down what medications or drinks taken on the day of the study so that the participant does not have to say this information out loud in order to protect privacy.

**10) Provisions to maintain the confidentiality of data**

- a) Initial data to be gathered by [name] or [name] include information regarding age, sex, past medical history (i.e. previous medical diagnoses), and medication usage (*See Attachment D*). This information will be linked to the participants' de-identified code. The code will only be linked back to the patient's name on a password-protected Excel sheet on the password-protected University computer belonging to the investigators.
- b) Blood pressure and heart rate readings will be linked to the participants' de-identified code. The code will only be linked back to the patient's name on a

UB HRP-503 TEMPLATE: Protocol

PROTOCOL TITLE: Investigating the short-term effects of *Passiflora incarnata* and mobile audio-guided meditation on blood pressure and heart rate in naturopathic medical students

PROTOCOL DATE: 3/28/19

Template Revised: June 14, 2010

- password-protected Excel sheet on the password-protected University computer belonging to the investigators.
- c) The adverse event survey (*See Attachment C*) will be linked to the participants' de-identified code. The code will only be linked back to the patient's name on a password-protected Excel sheet on the password-protected University computer belonging to the investigators.
  - d) Only [name] and [name] will have access to the participants' data. Student RAs will be recording blood pressure readings and heart rate data, but will not have access to the inclusion/exclusion checklist, initial data questionnaire, and adverse events questionnaire.
  - e) The initial questionnaire and the adverse event survey will be performed on paper and turned into the research team. Once the answers are transcribed to password protected Excel sheets, they will be stored in a locked file cabinet in [name] locked office for a period of 3 years. After this time, they will be shredded. These paper forms will contain only the subjects' de-identified code.
  - f) Signed consent forms will be stored in [name] locked office in a locked file cabinet.

**11) Medical care and compensation for injury**

- a) Participants can seek treatment at Student Health Services in relation to any adverse events experienced as a result of the treatment. Routine care should be covered by the participants' health insurance.

**12) Cost to subjects**

- a) Participants may incur a cost in the event that
  - i) They incur data usage charge for downloading and using the Headspace app
    - (1) Instructions will be given to the participants to use wifi to download and use the app to avoid this cost (*See Attachment E*)
  - ii) They purchase headphones to listen to the Headspace app

**13) Consent process**

- a) Once a participant expresses interest in participating and meets the eligibility criteria, he or she will meet with a member of the research team (i.e. [name] or [name]) to verbally review the consent document. Consent will take place in a clinic examination room or in the office of [name] or [name]. The consent process occurs before the research begins on a different day.
- b) Student RAs will not be involved in the consent process.
- c) The consent conversation will take about 20 minutes and should occur within a few days after informing the participant that he or she is eligible for participation in the study.
- d) The research team will make it **very** clear that the participant does not have to participate in this study and that participation is voluntary. It will be made very clear to the participant that he/she may withdraw at any time without any retaliation in the classroom, as [name] and [name] are instructors for these students in the naturopathic program. No extra credit will be given to students who choose to participate, and no "punishment" will be given to the students who

UB HRP-503 TEMPLATE: Protocol

PROTOCOL TITLE: Investigating the short-term effects of *Passiflora incarnata* and mobile audio-guided meditation on blood pressure and heart rate in naturopathic medical students

PROTOCOL DATE: 3/28/19

Template Revised: June 14, 2010

- choose not to participate. They will be assured that their willingness to participate in the research will in no way affect the way that they are treated in the classroom by their professors. They will be assured that choosing to participate or not to participate in the research will not affect their grade in their naturopathic classes.
- e) All participants must give consent and sign the consent form in order to participate in the research study.
  - f) Signed consent forms will be stored in [name] locked office in a locked file cabinet.

#### **14) Process to document consent in writing**

- a) Once a participant expresses interest in participating and meets the eligibility criteria, he or she will meet with a member of the research team (i.e. [name], [name], or Student Research Assistant) to verbally review the consent document. Consent will take place in a clinic examination room or in the office of [name] or [name].
- b) Participants may sign the consent document at that time, if they are comfortable, or they may think about it for a few days and sign the consent document at a later date. If more than a week has passed since the initial consent conversation, another consent conversation will occur to ensure that the participant remembers the details.

#### **15) Vulnerable populations**

- a) **The participants will be students in the naturopathic medical program, where [name] and [name] teach.**
- b) The research team will make it **very** clear that the participant does not have to participate in this study and that participation is voluntary. It will be made very clear to the participant that he/she may withdraw at any time without any retaliation in the classroom, as [name] and [name] are instructors for these students in the naturopathic program. No extra credit will be given to students who choose to participate, and no "punishment" will be given to the students who choose not to participate. They will be assured that their willingness to participate in the research will in no way affect the way that they are treated in the classroom by their professors. They will be assured that choosing to participate or not to participate in the research will not affect their grade in their naturopathic classes.
- c) Naturopathic students will not be recruited for the study during class time where the students are in class with [name] or [name].
- d) Pregnant woman are excluded from the study

#### **16) Drugs or Devices**

#### **17) Sharing of results with subjects**

- a) Results will not be shared with the subject unless
  - i) If the patient's average baseline or 15 minute blood pressure falls into the Stage I (130-139/80-89 mmHg) or Stage II (>140/>90 mmHg) hypertensive range, he/she will be given this information at the conclusion of the study period in private, so as not to have his/her classmates hear the information.

UB HRP-503 TEMPLATE: Protocol

PROTOCOL TITLE: Investigating the short-term effects of *Passiflora incarnata* and mobile audio-guided meditation on blood pressure and heart rate in naturopathic medical students

PROTOCOL DATE: 3/28/19

Template Revised: June 14, 2010

- ii)** If the patient's baseline or 15 minute heart rate falls into the bradycardic (<50 bpm) or tachycardic (>100 bpm), he/she will be given this information at the conclusion of the study period in private, so as not to have his/her classmates hear the information.

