#### 5) Resources available to conduct the Human Research

- The naturopathic medical program currently has 77 students, so we are aiming for a high participation rate from the students.
- Recruitment will take place from May 2019 until August 2019. We expect the research activity to take place during the Fall 2019 semester.
- The UB Naturopathic Clinic has 19 treatment rooms and 1 large classroom which provides ample space for the research to occur.
- We have one pulse-oximetry device for calculating heart rate
- We have five sphygmomanometers for performing manual blood pressure readings
- We need one 4oz. bottle of *Passiflora incarnata* solid extract by Wise Woman Herbals, which has been donated by the company.
- The co-investigators are:

UB HRP-503 TEMPLATE: Protocol

PROTOCOL TITLE: Investigating the short-term effects of *Passiflora incarnata* and mobile audio-guided meditation on blood pressure and heart rate in naturopathic medical students

PROTOCOL DATE: 3/28/19

Template Revised: June 14, 2010

- [name], ND has been associated with the UB Naturopathic Clinic for 3 years as a supervising physician. She has full knowledge of UB Naturopathic Clinic culture and policies.
  - [name], MD who has vast research experience both at UBSNM and at Yale.
  - [name] – Student Research Assistant, current first year ND student, has research and biology experience from Stonybrook University
  - [name] – Student Research Assistant, current second year ND student– has research experience from Eastern Connecticut State University
  - [name] – Student Research Assistant, current second year ND student– has research experience at the University of Bridgeport School of Naturopathic Medicine in the Anatomy Lab with [name]
- In the event of an adverse reaction to the *Passiflora incarnata* extract or the meditation, Student Health Services is available on the first floor of the Health Sciences Building
  - The research team will meet and have a training session before the research session occurs
  - All research team members are CITI-certified

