**c) Study Endpoints\***

i) **Primary endpoints:** Blood pressure readings in mm/Hg and heart rate in beats per minute (bpm)

(1) According to the American Heart Association, blood pressure readings are as follows:

(a) Normal: Less than 120/80mmHg

(b) Elevated: 120-129/<80 mmHg

(c) Stage I Hypertension: 130-139/80-89 mmHg

(d) Stage II Hypertension: >140/>90 mmHg

(e) Hypertensive Crisis: >180/>120 mmHg

ii) **Primary safety endpoints:** Adverse events will be recorded for both *Passiflora incarnata* extract and the audio-guided meditation

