**d) Procedures involved in the Human Research\***

i) This will be a randomized, double-blind, placebo controlled trial.

ii) Students will be randomized to Group I, II, or III before the study begins

UB HRP-503 TEMPLATE: Protocol

PROTOCOL TITLE: Investigating the short-term effects of *Passiflora incarnata* and mobile audio-guided meditation on blood pressure and heart rate in naturopathic medical students

PROTOCOL DATE: 3/28/19

Template Revised: June 14, 2010

- iii) Naturopathic medical students will come to the study area in groups of 15-25 (each naturopathic cohort will be studied on a different day)
- iv) Naturopathic medical students will be studied on the day of a classroom examination with three left arm seated blood pressure readings and one heart rate reading taken 15 minutes after the end of the exam and then 15 minutes after that.
- v) All participants will be instructed to download Headspace app onto their smartphone prior to the research date
- vi) The participants will be randomized into three groups
  - (1) Group I
    - (a) Baseline (15 minutes post-exam) blood pressure readings (three left arm seated readings, average will be calculated) and one heart rate reading taken after at least 5 minutes of rest time without talking, eating, or caffeine consumption.
    - (b) This group will not be given any intervention. Subjects will sit quietly for 15 minutes and can read a book, surf the internet, etc. Subjects may not consume caffeine, eat food, or listen to any meditation during this time.
    - (c) Three left arm seated blood pressure readings and one heart rate will be taken 15 minutes after the baseline reading.
  - (2) Group II
    - (a) Baseline (15 minutes post-exam) blood pressure readings (three left arm seated readings, average will be calculated) and one heart rate reading taken after at least 5 minutes of rest time without talking, eating food, or caffeine consumption.
    - (b) 15 minutes after classroom examination – will be given 1/4 tsp of blackstrap molasses placebo and a 10 minute audio-guided mobile meditation session via the Headspace App. Subjects may not consume caffeine or eat food during this time.
    - (c) Three left arm seated blood pressure readings and one heart rate will be taken 15 minutes after the baseline reading.
  - (3) Group III

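### The blood pressure disclosure bands in section 17 leave a hole between Stage I and Stage II, so an average of exactly 140/90 triggers no disclosure at that time point

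*Protocol*

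**What the plan says.** Section 17 of the protocol starts from non-disclosure: "Results will not be shared with the subject unless". Item a(i) then makes an exception when the participant's "average baseline or 15 minute blood pressure" "falls into the Stage I (130-139/80-89 mmHg) or Stage II (>140/>90 mmHg) hypertensive range". Section 6(c), Study Endpoints, carries the same limits: "Stage I Hypertension: 130-139/80-89 mmHg" and "Stage II Hypertension: >140/>90 mmHg".

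The value compared with the bands comes from repeated manual readings. Section 5 says "We have five sphygmomanometers for performing manual blood pressure readings", and section 6(d) defines the baseline in every group by "three left arm seated readings, average will be calculated". For the second time point section 6(d) says "Three left arm seated blood pressure readings and one heart rate will be taken 15 minutes after the baseline reading", without repeating that they are averaged.

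**The concern.** Two adjacent bands that both lead to the same action should meet. Here they do not: one closes at 139/89 and the next opens strictly above 140/90. Because the default is silence, a value in the hole is handled like a normal reading, although lower and higher pressures on either side of it are reported.

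What is at stake is participant information. Section 17 is the only rule in the protocol for telling someone about a raised pressure measured in the study. The adverse event follow-up in sections 6(d) and 6(f) starts from what participants report, not from measured pressure, so it does not close the hole.

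**Working it through.** **1. The rule applied as written.** The protocol does not say whether the slash means that either component suffices or that both must lie in the band, so both readings are shown.

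| Average | Either component | Both components |
|---|---|---|
| 139/89 | disclosed | disclosed |
| 139.33/89.33 | not disclosed | not disclosed |
| 139.67/89.67 | not disclosed | not disclosed |
| 140/90 | not disclosed | not disclosed |
| 141/91 | disclosed | disclosed |
| 140/75 | not disclosed | not disclosed |
| 125/90 | not disclosed | not disclosed |
| 140/85 | disclosed | not disclosed |
| 140/92 | disclosed | not disclosed |

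The hole at 140/90 does not depend on the reading of the slash. What happens when only one component is in the hole does.

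**2. Can these values occur?** A mean of three whole-number readings moves in steps of 1/3 mmHg. The uncovered means are 418/3 = 139.33, 419/3 = 139.67 and 420/3 = 140 systolic, and 268/3 = 89.33, 269/3 = 89.67 and 270/3 = 90 diastolic. If manual readings are taken to the nearest 2 mmHg, the sum of three is even, so 418/3 and 420/3 (268/3 and 270/3) can still arise. If the 15-minute value were not averaged, whole readings of 140 and 90 would still fall in no band.

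**3. How often?** The protocol gives no means or SDs, so every input here is an assumption:
- mean 118/76 or 125/80;
- between-person SD 12/9, with correlation 0.7 between systolic and diastolic;
- within-person SD 4/3 or 8/6, independent for each reading;
- three readings rounded to 1 or 2 mmHg and averaged at both time points;
- 15-minute change 0 or −5/−3 mmHg;
- either component in a band triggers disclosure.

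This makes 2 × 2 × 2 × 2 = 16 scenarios, each simulated. A value counts as raised if systolic is ≥130 or diastolic ≥80. It counts as caught if systolic is in 130–139 or >140, or diastolic is in 80–89 or >90. A participant is never informed if a raised value is missed at one or both time points and neither time point is caught.

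| Quantity | Range over scenarios |
|---|---|
| A component in the hole at baseline | 2.1–5.4% of participants |
| Of these, disclosed through the other component | 55–72% |
| Missed at baseline | 0.8–1.8% of participants |
| Of these, caught at 15 minutes | 76–93% |
| Never informed | 0.05–0.43% of participants |
| Exactly 140/90 at baseline | 0.004–0.04% of participants |

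A rough cross-check of the never-informed range multiplies the share missed at baseline by the share not caught later: 0.8% × (1 − 0.93) = 0.06% and 1.8% × (1 − 0.76) = 0.43%.

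**4. In people.** With the target of 70: 0.05% × 70 = 0.04 and 0.43% × 70 = 0.30. With the 45 that the protocol would accept: 0.05% × 45 = 0.02 and 0.43% × 45 = 0.19.

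**5. With contiguous bands.** If Stage I is 130 to <140 / 80 to <90 and Stage II is ≥140 / ≥90, all six uncovered averages fall in a band and 140/90 is disclosed on either reading of the slash. A mixed pair such as 140/85 is still disclosed only if either component suffices.

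**The case against.** The strongest reply is that this is a copy-edit. The stages on both sides of 140/90 are disclosed, so the action is the same whichever one 140/90 belongs to. The investigators include physicians, who would probably tell the participant anyway. The expected number left uninformed is well below one. All of that stands, and it fixes the point at minor. It does not make the stated rule correct: staff would have to depart from its wording to do what was evidently meant.

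A second reply is that the text was machine-read from PDF, and a ≥ sign may have lost its bar. That cannot be excluded, although the same sign appears in sections 6(c) and 17. It would settle exactly 140 and 90 but would leave 139.33, 139.67, 89.33 and 89.67 uncovered, since no rounding rule is given.

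A third reply concerns the slash, and it stands in full. The frequencies above assume that either component suffices. The remedy matters too: under the assumptions above, about 38–59% of participants have systolic ≥130 or diastolic ≥80 at baseline, against about 13–29% with both. If the slash was meant as both, an either-component rule would go well beyond closing the hole.

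The possibility that the 15-minute value is not averaged adds little. Section 17 can be read as applying the average to both time points, and 140 and 90 are uncovered either way.

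**Conclusion.** The point holds as a minor error in a stated decision rule. Followed literally, section 17 discloses 139/89 and 141/91 but not 140/90, and section 6(c) repeats the same limits. About 0.05–0.43% of participants would never be informed, given the assumed means and SDs and the either-component reading. Most likely nobody in this trial would be affected.

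Two stronger inferences are tempting, and neither is supported. One is that a participant at 140/90 is left uninformed. The rule fails at that time point only, and the other time point can still trigger disclosure. The other is that, because the bands sit under the primary endpoints, the gap damages the efficacy results or subject safety. The endpoints in section 6(c) are blood pressure in mmHg and heart rate in beats per minute, not the stages, and no dosing, eligibility, withdrawal or analysis step uses the bands.

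**What to change.** In section 17 a(i), make the bands contiguous: Stage I as 130 to <140 / 80 to <90 and Stage II as ≥140 / ≥90, applied to the unrounded average at baseline and at 15 minutes. Edit section 6(c) to match, for consistency only.

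State what the slash means. If either component is intended, the rule can be written simply as average systolic ≥130 or average diastolic ≥80 at either time point. If both are intended, say so, and say how a mixed pair such as 140/85 is handled.

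The cost is one wording change and a matching edit. Under the either-component reading the only consequence is an occasional extra private conversation. If the slash was meant as both, adopting the either-component rule would mean noticeably more disclosures, so that choice should be made deliberately.

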**b) Inclusion and Exclusion Criteria\***

i) **Inclusion criteria** – all naturopathic medical students are invited to participate

(1) Participants must have a smartphone with access to the Headspace application and headphones to listen to the session

ii) **Exclusion criteria**

(1) Those taking hypertensive medication

(2) Those taking anti-anxiety medication, including MAOI medication

(3) Those taking blood-thinning medication

(4) Those who are pregnant

(5) Those who could be pregnant

(6) Those who will have surgery 2 weeks before the research date

(7) Those who are scheduled to have surgery 2 weeks after the research date

(8) Those who do not have a smartphone or access to Headspace application

(9) Those who have consumed caffeine, food/tyramine containing foods, stimulant medication, cold medicine, decongestant medicine, antihistamine medicine, cough suppressants, alcoholic beverages, or stimulant energy drinks within 2 hours before the study period.

iii) Interested participants will be contacted by phone or in-person by one of the investigators ([name] or [name]) and screened for exclusion criteria

iv) We aim for 70 subjects to participate but can complete the research with 45-60 subjects to achieve 80-90% power, respectively.

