    - (a) Baseline (15 minutes post-exam) blood pressure readings (three left arm seated readings, average will be calculated) and one heart rate reading taken after at least 5 minutes of rest time without talking, eating, or caffeine consumption.
    - (b) 15 minutes after examination – will be given 1/8 tsp (900mg) of *Passiflora incarnata* solid extract by Wise Woman Herbals mixed with 1/8 tsp of blackstrap molasses to mask the taste and a 10 minute audio-guided mobile meditation session via the Headspace App. Subjects may not consume caffeine or eat food during this time.
    - (c) Three left arm seated blood pressure readings and one heart rate will be taken 15 minutes after the baseline reading.

UB HRP-503 TEMPLATE: Protocol

PROTOCOL TITLE: Investigating the short-term effects of *Passiflora incarnata* and mobile audio-guided meditation on blood pressure and heart rate in naturopathic medical students

PROTOCOL DATE: 3/28/19

Template Revised: June 14, 2010

vii) Safety considerations

- (1) All participants will be given a paper survey about adverse events (*see Attachment C*) which will be returned to the research team by the end of the same study day. Any participant who marks a moderate-severe adverse event will be followed up by [name] for appropriate management.
- (2) [name] phone number and contact information will be given to the study subjects so they can contact her in the event another adverse event arises after the survey has been returned.
- (3) The research will last for about 45 minutes. Three Blood pressure readings (all left arm seated) and one heart rate reading will be taken at baseline and again 15 minutes later.
- (4) Procedures taken to lessen the probability or magnitude of risks
  - (a) Adverse events related to *Passiflora incarnata* use have been found with chronic dosage. We attempt to minimize these risks by providing one-time acute dosage.
  - (b) We are attempting to minimize adverse events by excluding participants who are taking hypertensive medication, anti-anxiety medication, MAOI medication, or blood-thinning medication.
  - (c) We are attempting to minimize adverse events by excluding participants who are pregnant or may be pregnant.

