- i) [name] will evaluate the adverse events survey and follow up with any participant who experience a moderate-severe adverse event
  - ii) Participants will be encouraged to report additional adverse events to [name] directly in the days following the research even once the survey has been handed in.
- g) Withdrawal of subjects\***
- i) Participants can voluntarily withdraw at any time
  - ii) Once a participant has withdrawn from the research, his/her data will not be included in our analysis
  - iii) Withdrawal may occur without the participants' consent if:
    - (1) His/Her smartphone or Headspace application is not functioning within 30 minutes after the end of his/her classroom examination
    - (2) He/She did not take the classroom examination that day
    - (3) He/She eats food/tyramine containing food, stimulant medication, alcoholic beverages, cold medicine, decongestant medication, antihistamine medication, cough suppressant medication, stimulant energy drinks, or consume caffeine within 2 hours before the study period or during the study period.
- 7) Risks to subjects\***
- a) Privacy Risks**
- i) Since naturopathic medical students will be studied in groups in one large room, the subjects will be informed that his/her classmates in the same room will know that he/she is participating in the study.
  - b) To minimize any privacy risks, all medical information will be collected in private before the day of the study. On the day of the study, we will not read the participants' blood pressure and heart rate readings out loud. We also will ask the participant to write down what medications or drinks taken on the day of the study

UB HRP-503 TEMPLATE: Protocol

PROTOCOL TITLE: Investigating the short-term effects of *Passiflora incarnata* and mobile audio-guided meditation on blood pressure and heart rate in naturopathic medical students

PROTOCOL DATE: 3/28/19

Template Revised: June 14, 2010

so that the participant does not have to say this information out loud in order to protect privacy.

- c) **Inconveniences: Time Invested/Timing with Classroom Examination**
  - i) The participants may be inconvenienced by sparing 45 minutes after his/her classroom examination
  - ii) The participant may feel distracted during his/her examination in anticipation of the research taking place after the examination
    - (1) This is unlikely, as the research is intended to have a relaxing benefit on the participant

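### The protocol defines a hypertensive crisis band (>180/>120 mmHg) but attaches no action to it; a crisis-range baseline is disclosed only at the end of the session, after dosing

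*Protocol*

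**What the plan says.** - **Bands.** Section 6(c)(i) lists five blood pressure categories. The fourth is Stage II (>140/>90 mmHg, no upper limit) and the fifth is "Hypertensive Crisis: >180/>120 mmHg". The crisis category does not appear again.
- **Consequence of a high reading.** Section 17(a) withholds results from participants except in stated cases. Under 17(a)(i), someone whose average baseline or 15-minute pressure is in Stage I "or Stage II (>140/>90 mmHg) hypertensive range, he/she will be given this information at the conclusion of the study period in private". The reason given, that classmates should not overhear, explains the privacy but not the timing.
- **Order of events.** In section 6(d)(vi), step (a) is the baseline ("three left arm seated readings, average will be calculated") and step (b) is the intervention. In Group III the participant "will be given 1/8 tsp (900mg) of" the extract and then meditates. Step (b) carries no blood pressure condition, and no time is given for calculating the average.
- **Eligibility.** The exclusion in 6(b)(ii) that concerns blood pressure is "Those taking hypertensive medication". It sets no limit on the reading itself.
- **Withdrawal.** Section 6(g)(iii) opens with "Withdrawal may occur without the participants' consent if" and gives three grounds: phone or app failure, no exam that day, and forbidden food, drink or medicines.
- **Clinical follow-up.** Section 6(d)(vii)(1) says: "Any participant who marks a moderate-severe adverse event will be followed up by" a named clinician. The trigger is the participant's own survey answer.

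**The concern.** This is a matter of participant safety. Under section 9(d) student assistants take the readings, and the protocol gives them no instruction for a value that it labels a crisis itself. The one rule that does apply sets disclosure for the end of the session.

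The harm at issue is narrow. Nothing in the protocol suggests that the extract raises blood pressure: section 2 expects a fall, and section 3 cites an antihypertensive effect of a related plant in rats. What matters is the delay in telling and referring the participant, in all three groups. In Group III there is also the dose, of an extract for which section 3 says the authors know of no recent human trial on blood pressure.

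Protecting the second reading from an effect of disclosure would not justify the wait. A participant stopped at baseline has no second reading to protect and, once withdrawn, is not analysed under 6(g)(ii). After the 15-minute readings no measurement remains.

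**Working it through.** The protocol states no figure on this point, so there is none to reproduce. The check is a reading of the rules, followed by two small calculations.

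**1. What happens to a baseline average of, say, 185/125?**

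| Place a rule could sit | Does a blood pressure value trigger anything? |
|---|---|
| 6(a) and 6(b), eligibility | No. Medication use excludes; a value does not. Previous diagnoses are collected under 6(d)(vii)(5), but no rule excludes on them. |
| 6(d)(vi), steps (a) to (b) | No. Step (b) follows without a condition. |
| 6(d)(vii) and 6(f), safety follow-up | No. The trigger is a reported adverse event. |
| 6(g)(iii), withdrawal | No. None of the three grounds is blood pressure. |
| 5 and 11, Student Health Services | No. It is offered for adverse reactions or events. |
| 17(a)(i), sharing of results | Yes, but only disclosure at the end. |

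Since 185 > 140 and 125 > 90, the reading lies in the open-ended Stage II range and receives end-of-session disclosure. If the bands were read as mutually exclusive, the reading would be in neither Stage I nor Stage II and would not be disclosed at all. Neither reading leads to prompt action.

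**2. Length of the delay.** Baseline is at minute 15 after the exam (6(d)(iv)). The second readings are 15 minutes later, at minute 30. Participants give 45 minutes after the exam (7(c)(i)). A baseline result is therefore held for between 30 − 15 = 15 and 45 − 15 = 30 minutes, and that interval contains step (b).

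**3. Expected number of cases.** The protocol gives no mean or SD, so every input here is assumed. With normal tails, P(SBP > 180) + P(DBP > 120) is an upper bound for the rule that either limit is exceeded, whatever the correlation. Multiplying by 70, the recruitment target in section 4:

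| Assumed mean (SD), SBP / DBP | z, SBP / DBP | Sum of tails | × 70 |
|---|---|---|---|
| 120 (12) / 75 (9) | 5.00 / 5.00 | 2.9e-7 + 2.9e-7 = 5.7e-7 (rounded) | 0.00004 |
| 125 (15) / 78 (10) | 3.67 / 4.20 | 0.000123 + 0.000013 = 0.000136 | 0.0095 |
| 135 (18) / 85 (12) | 2.50 / 2.92 | 0.00621 + 0.00177 = 0.00798 | 0.56 |

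The protocol does not say whether both limits must be exceeded. If so, the smaller tail is an upper bound: 0.000013 × 70 ≈ 0.0009 for the middle row and 0.00177 × 70 ≈ 0.12 for the last.

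**4. Workload of a check.** Sessions have 15 to 25 participants, so there are 15 × 3 = 45 to 25 × 3 = 75 baseline readings. With five sphygmomanometers that is 15/5 = 3 to 25/5 = 5 participants per device. An average of three can exceed a limit only if at least one of the three readings does, so it need be worked out before step (b) only in that case.

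**The case against.** The strongest reply is that the five bands are a reference table attributed to the American Heart Association, not a set of action thresholds. On that view a crisis reading is covered by the open-ended Stage II rule, and only timing is in dispute. Continued dosing is inferred from silence: clinicians are on the team, nothing forbids them to act, and the content of the planned training session and the attachments is not shown. The delay is short and spent seated, with Student Health Services in the building, and the event is very unlikely.

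Much of this is right. The table alone contradicts nothing, the protocol never says in words that dosing continues, and a clinician might well step in. The highest frequency assumes a sample mean already in Stage I, which is not what one expects of students who take no hypertensive medication. But the sponsor did write a rule for high blood pressure, and that rule directs disclosure to the end. Staff who follow it would take a participant with a crisis reading through the intervention. The right to withdraw voluntarily does not help someone who has not been told.

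Three further objections bear on the remedy. Taking a student out of a shared room is visible to classmates; that is a real cost, which a treatment room reduces but does not remove. A repeat reading before stopping is already built in, because the rule uses the average of three. Heart rate has the same end-of-session disclosure (17(a)(ii)), although the one serious cardiovascular event cited in section 3 is ventricular tachycardia. That is a fair observation, but the protocol defines no crisis level for heart rate, and the point does not weaken the case on blood pressure.

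**Conclusion.** The concern holds. The protocol labels a blood pressure range a crisis and attaches no action to it. The only rule that reaches such a reading postpones disclosure by about 15 to 30 minutes, past the intervention. All three groups are affected by the delay; only Group III would also take the extract.

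The event is expected to be very rare: at most about 0.0095 cases among 70 under the middle assumptions, with a wide range (0.00004 to 0.56) because the documents supply no means or SDs. The conclusion does not depend on those figures. It rests on the text of the rules, the seriousness of a single such reading, and the small cost of acting on it. The protocol should be changed, but the gap does not undermine the trial's design. A stop-and-refer rule is protocol content, so an unseen statistical analysis plan would not supply it.

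**What to change.** Amend three sections, for the crisis band only. The Stage I, Stage II and heart rate rules can stay as they are.

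1. **6(d)(vi), step (a), all three groups.** Check the three baseline readings before step (b), and calculate the average on the spot if any reading exceeds a limit. If the average is systolic >180 or diastolic >120 mmHg, the participant does not go on to step (b), is told at once in private (for example in a treatment room), and is referred to the responsible clinician or Student Health Services. Stating *or* also removes the ambiguity in the band.
2. **17(a)(i).** Name the crisis band and require immediate private disclosure for both the baseline and the 15-minute readings.
3. **6(g)(iii).** Add a crisis-range baseline as a ground for withdrawal.

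Because "Students will be randomized to Group I, II, or III before the study begins", these will be exclusions after randomisation but before treatment. The same rule should apply to every group, and the cases should be reported by group.

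The cost is a short amendment and a brief check of 45 to 75 readings per session, using existing equipment and rooms. Very rarely, one participant will visibly leave the session and, under 6(g)(ii), will not be analysed.
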